3.4 Duration of Patient Participation

Patients will continue to receive NUC-1031 until the occurrence of disease progression by RECIST or unmanageable drug-related adverse events despite dose modification. Patients may also decline treatment at any time for any reason, or they may meet any of the other reasons for treatment withdrawal defined in [Section 6.1](#). Reasons for treatment discontinuation must be captured in the patient medical record and on the Treatment Discontinuation page of the CRF.

Should a patient discontinue treatment without radiological evidence of disease progression, the patient should continue to undergo tumor assessment every 8 weeks from C1D1 until such time as progression can be documented or new treatment is initiated.

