5.5.8 Follow-Up

Patients who stop treatment with no evidence of disease progression as defined by RECIST criteria will continue to receive scans at regular intervals (every 8 weeks [± 7 days] from C1D1) until disease progression or death (whichever comes first) in order to determine duration of overall response and PFS.

Patients with evidence of disease progression as defined by RECIST criteria will receive a phone call at regular intervals (every 12 weeks [± 7 days]) until death, loss to follow-up, or study discontinuation in order to determine duration of Overall Survival.

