11 TUMOR RESPONSE ASSESSMENTS

11.1 Tumor Measurements and Assessment of Disease Response

Patients must have at least one lesion that can be accurately assessed at baseline by CT, MRI or PET-CT (US only), which is suitable for repeated assessment in order to be eligible for this study. All known or suspected disease sites must be assessed at baseline by either CT, MRI or PET-CT (US only) scan. The same radiological methods at baseline must be used to follow lesions throughout the study. Disease must be measured according to RECIST criteria, with target and non-target lesions identified, measured and followed throughout the study ([Appendix 2](#)). Biopsied lesions should not be designated as target lesions for the purposes of RECIST.

Whenever possible, the same qualified physician will interpret results to reduce variability. Radiographic images will be maintained at the study center, and Investigator's findings will be filed in the patient's source documents.

In addition, digital copies of all radiographic images will be collected and stored in a central radiologic facility in order to allow for independent confirmation of the radiographic imaging results. Instructions for the collection, and submission of images are provided in a separate Imaging Manual.

Tumor measurements and disease response assessments are to be performed every 8 weeks (± 7 days) from C1D1. If the patient stops study treatment for reasons other than radiologically confirmed PD, tumor measurements and disease response assessments should continue every 8 weeks (± 7 days) from C1D1 thereafter until PD is radiologically confirmed.

Tumor measurements and disease response assessments also are to be performed any time disease progression is suspected.

Patients should not discontinue NUC-1031 because of raised CA125 or other clinical signs of PD until PD has been confirmed by RECIST.

CRs and PRs must be confirmed by repeated images at least 4 weeks after initial documentation.

In the case of SD, measurements must have met the SD criteria at least once after study entry at a minimum interval of not less than 6 weeks.

A third-party central imaging vendor will review all study-related imaging. The imaging vendor will not be responsible for assessing images in real-time to inform on patient treatment decisions. This responsibility will remain with the Principal Investigator at the site. Please refer to the Imaging Manual for details on submission and review of images.

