13.5.4 Efficacy Analysis

The primary response evaluation is based upon the determination of response using RECIST ([Appendix 2](#)) by a BICR:

- **ORR** is defined as the number of patients achieving a confirmed response (CR or PR). Number and percentage of patients achieving a response, with confidence intervals, will be provided. In addition, the number and percentage of patients achieving individual best response criteria of CR, PR, SD, PD, or NE will be described.
- **Change from baseline in tumor size** is measured as the percentage change in the total measurements of target lesions from the pre-treatment scan, measured at each scheduled scan.
- **Duration of Overall Response** is measured from the time measurement criteria are first met for CR or PR (whichever is first recorded) until the first date that recurrent or PD is objectively documented (taking as reference for PD the smallest measurements recorded since the treatment started). Only responses that were later confirmed, will be considered when calculating the DoR. For patients who were lost to follow-up without progression or reached the time point of analysis without a known record of death or progression, the duration of response will be censored at the date of last tumor assessment.
- **PFS** is defined as the time from the date of study treatment initiation (start of treatment) to the first date of objectively determined PD or death from any cause. For patients who are still alive at the time of the data cut-off date and without evidence of tumor progression, PFS will be censored at the date of the most recent objective progression-free observation. For patients who receive subsequent anticancer therapy prior to objective disease progression or death, PFS will be censored at the date of the last objective progression-free observation prior to the date of subsequent therapy.

The number of overall censored patients, number of patients with events and Kaplan-Meier estimates median time will be provided. In addition, the results will be presented graphically in Kaplan-Meier plots.

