Cytology, Histology – these techniques can be used to differentiate between PR and CR in rare cases if required by protocol (for example, residual lesions in tumor types such as germ cell tumors, where known residual benign tumors can remain). When effusions are known to be a potential adverse effect of treatment (e.g. with certain taxane compounds or angiogenesis inhibitors), the cytological confirmation of the neoplastic origin of any effusion that appears or worsens during treatment when the measurable tumor has met criteria for response or stable disease is advised to differentiate between response or stable disease and progressive disease.

Tumor Response Evaluation

All patients will have their BEST RESPONSE from the start of study treatment until the end of treatment classified as outlined below. Complete or PRs may be claimed only if the criteria for each are met at a subsequent time point at least 4 weeks later. Refer to the [Tables 1](#) and [2](#) below.

Complete Response (CR) – disappearance of all *target* and *non-target* lesions and normalization of tumor markers. Pathological lymph nodes must have short axis measures <10 mm (Note: continue to record the measurement even if <10 mm and considered CR). Tumor markers must have normalized. Residual lesions (other than nodes <10 mm) thought to be non-malignant should be further investigated (by cytology or PET scans) before CR can be accepted.

Partial Response (PR) – at least a 30% decrease in the sum of measures (longest diameter for tumor lesions and short axis measure for nodes) of target lesions, taking as reference the baseline sum of diameters. Non-target lesions must be non-PD.

Stable Disease (SD) – neither sufficient shrinkage to qualify for PR nor sufficient increase to qualify for PD taking as reference the smallest sum of diameters on study.

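### Appendix 2 ends the best-response window at end of treatment, while Section 11.1 keeps assessing response after treatment stops, so it is unclear which off-treatment scans count towards the primary ORR

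*Protocol*

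**What the plan says.** Section 13.5.4 opens the efficacy analysis with "The primary response evaluation is based upon the determination of response using RECIST" and cites Appendix 2 directly after. It then defines ORR as confirmed CR or PR and gives no time window.

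Appendix 2, under Tumor Response Evaluation, supplies the only best-response window in the protocol: "All patients will have their BEST RESPONSE from the start of study treatment until the end of treatment classified as outlined below". The next sentence sets the confirmation rule: "Complete or PRs may be claimed only if the criteria for each are met at a subsequent time point at least 4 weeks later". That sentence does not say whether the patient must still be on treatment at the second time point.

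Section 11.1 covers patients who come off drug without progression: "If the patient stops study treatment for reasons other than radiologically confirmed PD, tumor measurements and disease response assessments should continue every 8 weeks". Section 3.4 says the same in other words, and ends these scans at documented progression or at the start of another treatment. Section 5.5.8 also keeps scanning these patients, but gives the purpose and end point as "until disease progression or death (whichever comes first) in order to determine duration of overall response and PFS".

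Section 13.1 sets success at 4 or more confirmed responses in 44 patients. Section 13.5.7 places the primary analysis about 16 weeks after the 44th patient starts treatment.

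**The concern.** Two parts of the protocol use different clocks for response. Appendix 2 ties best response to the treatment period. Section 11.1 ties assessment to a calendar from Cycle 1 Day 1 and carries it past the last dose. Appendix 2 itself leans the same way elsewhere: it asks for assessments on a calendar schedule not shifted by treatment delays, and for every included patient to be assessed for response even after a major treatment deviation.

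Stopping without progression is foreseen. Section 6.1 lists several reasons, among them toxicity, intercurrent illness and withdrawal from treatment. For such patients the protocol collects response data and then, on the literal wording, discards at least part of them. Two competent readers could classify the same patient differently in the primary endpoint, and the threshold is low enough for one classification to matter.

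**Working it through.** **1. The passages applied to two patients.** Visit windows are ignored and Cycle 1 Day 1 is day 1, so the 8-week scan falls on day 57 and the 16-week scan on day 113.

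- *Response first reached off treatment.* A patient has SD at day 57, stops without progression, meets PR at day 113 and is confirmed at least 4 weeks later. Section 11.1 schedules these scans. Appendix 2 closes the window before day 113, so best response stays SD. The literal text excludes this patient.
- *Response first reached on treatment, confirmed off treatment.* A patient receives Cycle 3 Day 1 on day 57, has PR on that day's scan, and then stops. Confirmation is possible from day 57 + 28 = 85; the next routine scan is day 113. If end of treatment means last dose, the window closes on day 57 and both dates fall outside it. If it means the End of Treatment visit (within 30 ± 7 days of last dose, Section 6.1), the window closes by day 57 + 30 = 87, at the latest day 94. A confirming scan on day 85 could then fall inside it, but the one on day 113 could not. If the window applies only to the first documentation and not to confirmation, the patient is a responder on either date. The text does not choose between these readings.

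**2. The plan's own figures.** Inputs from Section 13.1: n = 44, success at 4 or more responses, true ORR 15% or 5%.

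P(X ≥ 4) = 1 − Σ C(44,k) p^k (1−p)^(44−k), k = 0 to 3.

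At p = 0.15: 1 − (0.0008 + 0.0061 + 0.0231 + 0.0571) = 0.913, which agrees with the stated value of more than 80%. At p = 0.05 the result is 0.177, which does not agree with the stated value of less than 7%. A rule of 5 or more gives 0.067 at 5% and 0.810 at 15%, matching both stated figures. That discrepancy is a separate matter; the rule as written, 4 or more, is used below.

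**3. Sensitivity to lost responders.** Let f be the share of true confirmed responders not counted because of the window. The documents give no value for f, so a range is shown. The counted rate is p(1 − f).

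| f (assumed) | Counted rate if true ORR is 15% | P(≥ 4 of 44) | P(≥ 4 of 44) if true ORR is 5% |
|---|---|---|---|
| 0 | 0.150 | 91.3% | 17.7% |
| 10% | 0.135 | 86.2% | 13.5% |
| 20% | 0.120 | 79.0% | 9.8% |
| 30% | 0.105 | 69.2% | 6.7% |

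**4. Weight of one patient.** At p = 0.15, P(X = 4) = P(X ≥ 4) − P(X ≥ 5) = 0.913 − 0.810 = 0.103. In about one trial in ten the count would be exactly 4, and losing a single responder would turn success into failure.

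**The case against.** The strongest reply is that Appendix 2 calls itself a quick reference, that ORR is defined in Section 13.5.4 without a window, and that the confirmation rule, repeated in Section 11.1 and the Appendix 2 tables, never asks for an on-treatment scan. Much of this stands, and it limits what can be claimed.

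- A reader might infer that a PR at week 8, confirmed at week 16 after stopping for toxicity, is definitely a non-responder. The documents do not establish that. The window sentence governs classification of best response; the confirmation sentence is separate and unrestricted. The case is ambiguous.
- A reader might take Section 5.5.8 as contradicting an ORR window that ends with treatment. It does not: it names duration of response and PFS as the purpose, not ORR. The passage in tension with Appendix 2 is Section 11.1, which calls these scans response assessments.
- A reader might say that nothing stops responses being counted after new anti-cancer therapy. That arises only if the window is ignored. Footnote 21 of the Summary Schedule of Events, Section 3.4, the heading of Section 5.5.6 and Section 6.2 all end scanning at new treatment; Sections 5.5.8 and 11.1 omit that limit.
- The loss rates are assumptions. At 10% the rule still meets the stated power of more than 80%. Nothing in the documents shows that losses would fall mainly on patients stopping for toxicity.

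The reply does not remove the problem. Section 13.5.4 cites Appendix 2 and offers no window of its own, so its silence cannot displace the one window the protocol states.

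**Conclusion.** The concern holds in a limited form. The protocol states a best-response window that, read literally, excludes responses first reached on scans it has itself scheduled, and leaves open whether off-treatment scans can confirm earlier responses. This is an inconsistency in stated text, not detail left for the SAP.

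Its size cannot be fixed from the documents. If 10% to 20% of responders went uncounted, the probability of success at a true ORR of 15% would be 86.2% to 79.0% instead of 91.3%. This assumes that 15% is the rate with all confirmed responses counted, that loss is independent between patients, and that the rule is 4 or more of 44. If the 15% was meant as an on-treatment rate, there is no loss of power against the design, but the ambiguity in classification remains. The point should be corrected before the primary analysis; it does not undermine the design.

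**What to change.** In Section 13.5.4 and Appendix 2, define best overall response, including the confirming scan, from first dose until the first of documented progression or start of new anti-cancer therapy, whether or not NUC-1031 has stopped. Reconcile Sections 5.5.8 and 11.1 with footnote 21 of the Summary Schedule of Events and Sections 3.4 and 6.2, so that follow-up scans stop being used for response at the same event throughout.

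The cost is a sentence in two places plus the alignment of two sections. The scans are already planned, and the new-therapy limit already appears in Section 3.4 and in the PFS censoring rule of Section 13.5.4. The small downside is that some counted responses will be reached or confirmed after dosing has ended. A sensitivity analysis restricted to on-treatment scans, with end of treatment defined, would show how much of the ORR depends on them.

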Appendix 2. Table 1. Integration of Target, Non-Target and New Lesions into Response Assessment

Target Lesions	Non-Target Lesions	New Lesions	Overall Response	Best Response for this Category Also Requires
Patients with target lesions \pm non-target lesions				
CR	CR	No	CR	Normalization of tumor markers All tumor nodes <10 mm Documented at least once ≥ 4 weeks from baseline
CR	Non-CR/Non-PD	No	PR	Documented at least once ≥ 4 weeks from baseline
CR	Not all evaluated	No	PR	
PR	Non-PD/ not all evaluated	No	PR	
SD	Non-PD/ not all evaluated	No	SD	
Not all evaluated	Non-PD	No	NE	
PD	Any	Any	PD	
Any	PD	Any	PD	
Any	Any	Yes	PD	

Note: Patients with a global deterioration of health status requiring discontinuation of treatment without objective evidence of disease progression (or evidence of unequivocal disease progression) at that time should be reported as “symptomatic deterioration”. This is a reason for stopping therapy, but is NOT objective PD. Every effort should be made to document the objective progression even after discontinuation of treatment.
				

Complete or partial responses may be claimed only if the criteria for each are met at a subsequent time point at least 4 weeks later. The best overall response can be interpreted from Appendix 2 [Table 2](#) on the next page.

Appendix 2. Table 2. Response Assessment after Subsequent Scan

Response: First Time Point	Subsequent Time Point	BEST Overall Response	Also Requires
CR	CR	CR	Normalization of tumor markers. All tumor nodes <10 mm.
CR	PR	SD, PD or PR (see comment*)	
CR	SD	SD provided minimum criteria for SD duration met, otherwise, PD	
CR	PD	SD provided minimum criteria for SD duration met, otherwise, PD	
CR	NE	SD provided minimum criteria for SD duration met, otherwise NE	
PR	CR	PR	
PR	PR	PR	
PR	SD	SD	
PR	PD	SD provided minimum criteria for SD duration met, otherwise, PD	
PR	NE	SD provided minimum criteria for SD duration met, otherwise NE	
NE	NE	NE	

* May consider PR providing initial "CR" likely PR on subsequent review – then original CR should be corrected. Recurrence of lesion after true CR is PD.

Frequency of Tumor Re-Evaluation

Tumors should be assessed at the end of every 2nd cycle.

Date of Progression

This is defined as the first day when the RECIST (v1.1) criteria for PD are met.

Reporting of Tumor Response

All patients included in the study must be assessed for response to treatment, even if there is a major protocol treatment deviation or if they are ineligible, or not followed/re-evaluated. Each patient will be assigned one of the following categories: complete response, partial response, stable disease, progressive disease, early death from malignant disease, early death from toxicity, early death from other cause or unknown (not assessable, insufficient data).

'Early death' is defined as any death occurring before the first per protocol time point of tumor re-evaluation. The responsible investigator will decide if the cause of death is malignant disease, toxicity or other cause. Patients for whom response is not confirmed will be classified as "unknown", unless they meet the criteria for stable disease (or the criteria for partial response in case of an unconfirmed complete response). Patients' response will also be classified as "unknown" if insufficient data were collected to allow evaluation per these criteria.

Appendix 3: FOSI-18 Questionnaire

Below is a list of statements that other people with your illness have said are important.
Please circle or mark one number per line to indicate your response as it applies to the past 7 days.

			Not at all	A little bit	Some-what	Quite a bit	Very much
D R S P	GP1	I have a lack of energy	0	1	2	3	4
	GP4	I have pain	0	1	2	3	4
	GP6	I feel ill	0	1	2	3	4
	O3	I have cramps in my stomach area	0	1	2	3	4
	HI7	I feel fatigued	0	1	2	3	4
	Cx6	I am bothered by constipation	0	1	2	3	4
	O1	I have swelling in my stomach area	0	1	2	3	4
	C3	I have control of my bowels	0	1	2	3	4
	GF5	I am sleeping well	0	1	2	3	4
	GE6	I worry that my condition will get worse	0	1	2	3	4
D R S E	GP2	I have nausea	0	1	2	3	4
	B5	I am bothered by hair loss	0	1	2	3	4
	GP5	I am bothered by side effects of treatment	0	1	2	3	4
	O2	I have been vomiting	0	1	2	3	4
	BTM15	I am bothered by skin problems	0	1	2	3	4

F W B	BMT5	I am able to get around by myself	0	1	2	3	4
	GF3	I am able to enjoy life	0	1	2	3	4
	GF7	I am content with the quality of my life right now	0	1	2	3	4

Appendix 4: EQ-5D-5L Questionnaire

Under each heading, please tick the ONE box that best describes your health TODAY.

MOBILITY

I have no problems in walking about

I have slight problems in walking about

I have moderate problems in walking about

I have severe problems in walking about

I am unable to walk about

SELF-CARE

I have no problems washing or dressing myself

I have slight problems washing or dressing myself

I have moderate problems washing or dressing myself

I have severe problems washing or dressing myself

I am unable to wash or dress myself

USUAL ACTIVITIES (e.g. work, study, housework, family or leisure activities)

I have no problems doing my usual activities

I have slight problems doing my usual activities

I have moderate problems doing my usual activities

I have severe problems doing my usual activities

I am unable to do my usual activities

PAIN/DISCOMFORT

I have no pain or discomfort

I have slight pain or discomfort

I have moderate pain or discomfort

I have severe pain or discomfort

I have extreme pain or discomfort

ANXIETY/DEPRESSION

I am not anxious or depressed

[figure not shown]
I am slightly anxious or depressed

I am moderately anxious or depressed

I am severely anxious or depressed

I am extremely anxious or depressed

- We would like to know how good or bad your health is TODAY.
- This scale is numbered from 0 to 100.
 - 100 means the best health you can imagine.
 - 0 means the worst health you can imagine.
- Mark an X on the scale to indicate how your health is TODAY.

Now, please write the number you marked on the scale in the box below.

YOUR HEALTH TODAY =

Appendix 5: ECOG Performance Scale

Activity Performance Description	Score
Fully active, able to carry out all on all pre-disease performance without restriction.	0
Restricted in physically strenuous activity but ambulatory and able to carry out work of a light or sedentary nature, e.g. light housework, office work.	1
Ambulatory and capable of all self-care, but unable to carry out any work activities. Up and about more than 50% of waking hours.	2
Capable of only limited self-care. Confined to bed or chair more than 50% of waking hours.	3
Completely disabled. Cannot carry out any self-care. Totally confined to bed or chair.	4
Dead	5
